Statistical analysis plan

Randomized Clinical Trial Evaluating the Impact of E-cigarette Device Warnings

NCT05714982

2/7/2023, Edited 6/24/2024

Hypotheses

This trial evaluates the impact of e-cigarette health warnings by randomly assigning vapers to have their devices and refills labeled with control messages, text warnings, or pictorial warnings.

The primary hypotheses are about the main trial outcome of vaping quit intentions across the 4 weeks of the trial. We hypothesize that text warnings will elicit higher vaping quit intentions than control messages. We also hypothesize that pictorial warnings will elicit higher vaping quit intentions than text warnings.

For secondary outcomes, we hypothesize that text warnings will elicit higher consumer understanding, information seeking and sharing, and vaping behavior change than control messages, and that pictorial warnings will elicit higher scores on these measures than text warnings. We do not have hypotheses about the impact of the warnings on unintended effects.

Analytic plan

Statistical analyses will use two-tailed tests and a critical alpha of .05.

Primary trial outcome

Vaping quit intentions will be measured using a 3-item scale at 5 time points: post-labeling (Visit 1) and at 1, 2, 3, and 4 weeks (Visits 2-5). The 3 items will be averaged to create a composite quit intention score for each time point. The primary trial outcome will be an average vaping quit intentions score across the 5 time points (i.e., grand mean of quit intentions). We will use all available data in computing 1) the quit intention score at each time point and 2) the aggregate quit intention score across time points. Because the quit intention survey items are forced response, missingness will be uncommon, and the use of two layers of averaging will naturally address most missingness. In the unexpected situation of having no intentions data for a participant, we will set their value to the grand mean for the trial overall (ignoring trial arm).

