We will estimate a general linear model with quit intentions as the continuous outcome and trial arm as a 3-level categorical, between-subjects predictor (pictorial, text, control; text arm will be the reference group). We will not adjust for demographic or other baseline characteristics per CONSORT recommendations (Consort, 2010). We will examine the following variables measured pre-randomization as potential moderators by adding categorical main effects for these terms and their interaction with trial arm: age, education, income, gender, sexual orientation, race, vaping frequency (some days or every day), and current cigarette smoking status. We will probe statistically significant interactions by examining the effect of trial arm within strata of the moderator, using Bonferroni corrections for the post-hoc tests.

We estimated sample size for a 3 arm trial using the following inputs: 80% power, α set at .05, an effect size Cohen's *d* of .16, number of measurements set at 4.2 time points (estimated average number of completed sessions based on our previous cigarette pack labeling trial; Brewer et al., 2016), and an interclass correlation (ICC) of .7 (based on an observed ICC in that trial; Brewer et al., 2016). The previous effect size estimate is based on the average observed *d* in two online experiments (Brewer et al., 2019; Brewer et al., in prep) between pictorial vs text warnings; control vs. text comparisons were larger in these two experiments.

For descriptive purposes, we will examine mean vaping quit intentions at each trial visit, calculating the mean and standard error. We will compare the trial arms graphically at each time point, examining whether means for each trial arm fall outside of the confidence interval for the other arms.

Secondary trial outcomes

Except as noted below, we will again estimate a general linear model for each secondary outcome shown in Table 1, with trial arm as a 3-level categorical, between-subjects predictor (pictorial, text, control; text arm will be the reference group). We will handle missingness as we did for the primary outcome.

Vaping quit attempt and cigarette smoking quit attempts will each be dichotomous outcomes (any quit attempt during the trial). We will estimate a logistic regression model with quit attempt as the outcome and trial arm as the categorial predictor with text arm as the reference group.

Construct	Variable type, range
Consumer understanding	
Knowledge	Continuous, 0-100%

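### The SAP gives neither the test nor the N behind its sample size; on its own inputs, ~1,200 participants give about 73% power, not 80%, for pictorial vs text.

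*SAP*

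**What the plan says.** The sample size paragraph (SAP, Analytic plan, Primary trial outcome) begins "We estimated sample size for a 3 arm trial using the following inputs: 80% power, α set at .05". The remaining inputs are "an effect size Cohen's *d* of .16", "number of measurements set at 4.2 time points" and "an interclass correlation (ICC) of .7". The paragraph does not say which test was sized and does not report the N that resulted.

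The same paragraph says where the effect size comes from: it is the average effect seen in two online experiments "between pictorial vs text warnings; control vs. text comparisons were larger in these two experiments".

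Three other places fix how that effect will be tested:

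- SAP, Hypotheses, second primary hypothesis: "We also hypothesize that pictorial warnings will elicit higher vaping quit intentions than text warnings".
- SAP, Analytic plan: "Statistical analyses will use two-tailed tests and a critical alpha of .05".
- SAP, primary outcome model: a general linear model with three-level trial arm, in which "text arm will be the reference group". Pictorial vs text is therefore one of the model's two direct coefficients.

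The only sample size is ~1,200, in the protocol synopsis (Number of Subjects). The synopsis refers to the SAP for statistics. The protocol's Randomization paragraph gives the three arms equal allocation, so about 400 per arm.

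**The concern.** The documents fix the contrast, the effect size, the alpha, the sidedness and the model. A reader will naturally take the 80% as the power for the contrast to which d = .16 belongs. If ~1,200 does not deliver that, the trial runs a higher false-negative risk than listed on the primary comparison for which the SAP expects the smaller effect. This matters most when a null pictorial-vs-text result has to be interpreted. The SAP alone does not reveal the gap, because it states neither the N nor the sizing test.

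**Working it through.** **Inputs.** From the SAP: two-tailed alpha .05, target power 80%, d = .16, m = 4.2 measurements, ICC = .7. From the protocol: N of about 1,200, equal allocation, so n = 400 per arm.

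**Assumptions.** d is in SD units of a single measurement, which is what entering a number of measurements and an ICC implies. Correlation is compound symmetric. Every participant contributes 4.2 measurements.

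**Step 1: variance of the averaged score**, relative to a single measurement.

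V = (1 + (m − 1) × ICC)/m = (1 + 3.2 × .7)/4.2 = .7714

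**Step 2: can ~1,200 be recovered?** A three-group omnibus F test with f = d/2 = .08 has noncentrality N × f²/V. At N = 1,200 this is 1,200 × .0064/.7714 = 9.96 on 2 and 1,197 df, which gives 81.3% power; 80% is reached at N = 1,165. This is a plausible origin for ~1,200, but the documents do not state it.

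**Step 3: N for the two-tailed pictorial-vs-text contrast.**

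n per arm = 2 × (1.960 + .8416)² × V/d² = 2 × 7.849 × .7714/.0256 = 473.0

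That is 1,419 in total. The noncentral t gives 474 per arm, 1,422 in total, about 220 more than ~1,200.

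**Step 4: power at 400 per arm.**

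SE = √(2 × .7714/400) = .0621, and .16/.0621 = 2.576

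Power = Φ(2.576 − 1.960) = .731; noncentral t with 1,197 df gives .730.

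**Step 5: effect detectable with 80% power at 400 per arm.**

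d = 2.8016 × .0621 = .174

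**Step 6: simulation.** The three-arm model with 4 or 5 sessions per person averaging 4.2 and ICC .7 gives 73.7% (20,000 runs, SE 0.3).

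**Step 7: sensitivity of power for pictorial vs text at d = .16.**

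| Change from the base case | Power |
|---|---|
| None | 73.0% |
| Total N 1,150 / 1,250 | 71% / 75% |
| m = 4 / m = 5 | 72.9% / 73.7% |
| ICC .6 / ICC .8 | 77% / 69% |
| 80% complete five sessions, 20% complete one (V = .8 × .76 + .2 × 1 = .808) | 71% |
| d on the averaged-score scale (V = 1) | 62% |

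In the last row, 80% power needs 614 per arm (1,842 in total), and the detectable d at 400 per arm is 2.8016 × √(2/400) = .198. Holding the other inputs, an ICC of about .54 would be needed for 80% power at 400 per arm.

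**Step 8: where the shortfall lies.** The SAP expects a larger effect for text vs control but gives no value. With illustrative values, power at 400 per arm is 83% for d = .18 and 90% for d = .20. If the arm means were 0, .16 and .32 (a lower bound for the ordering the SAP expects), then f = .16 × √(2/3) = .131 and omnibus power at 1,200 is 99.8%. A well-powered omnibus test therefore says little about pictorial vs text.

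**The case against.** The best defence is that nothing printed is contradicted. The SAP lists 80% as an input for a three-arm trial, and neither document claims that ~1,200 gives 80% for pictorial vs text. Nor does either call ~1,200 the output of this calculation; it could be a rounded target or a practical limit. The omnibus reading gives N = 1,165, and on that reading the sizing met its target. Finally, 73% depends on a scale for d that the SAP does not state, so only the direction is secure.

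Much of this stands as a limit on the point. There is no arithmetic slip, the origin of ~1,200 is inferred, and the exact power depends on assumptions. It does not remove the shortfall:

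- The synopsis sends the reader to the SAP for statistics, and no N from 1,150 to 1,250 takes the contrast above 75%.
- The SAP states no omnibus hypothesis. Both primary hypotheses are pairwise, and f = d/2 is the two-group conversion.
- The alternative scale for d makes the power worse, not better.
- One-sided sizing would give about 82% at 400 per arm, but it conflicts with the SAP's two-tailed rule.

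**Conclusion.** The concern holds. Under the SAP's own inputs, ~1,200 participants give about 73% power for the two-tailed pictorial-vs-text contrast at d = .16. The false-negative risk is about 27%, against the 20% implied by the listed power. That power is below 80% is well supported: it holds across the plausible readings of N, number of sessions and scale of d, and for ICCs from .6 to .8. The exact figure is less certain. It rests on d being on the single-measurement scale and on an ICC of .7, and runs from 62% to 77% as these vary. The problem is a mismatch between the sizing as described and the hypothesis test, together with an unstated test and N. Text vs control is less affected if its effect is larger, as the SAP expects. Type I error and bias are not involved.

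**What to change.** In the SAP's sample size paragraph, state N, the test used for sizing and the scale of d, and restate the power. If d is on the single-measurement scale, suitable wording is:

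> With ~1,200 participants (about 400 per arm), power is about 73% for d = .16 on the two-tailed pictorial-vs-text contrast; 80% power is reached at d = .174.

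If d refers to the averaged score, the corresponding figures are about 62% and d = .198. If an omnibus test was used for sizing, say so and give the pairwise power beside it.

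The cost is SAP wording only; enrolment, model and estimand are unchanged. The downside is that the stated power for pictorial vs text becomes less favourable, about 73% beside the listed 80%.

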This trial will assess the impact of e-cigarette warnings on vapers' devices and refills in a randomized clinical trial.

Recruitment: Vapers will first undergo screening online or call the study center to complete the screening survey over the phone. Trial staff will schedule eligible vapers for 2 in-person visits. For each of the 2 visits, vapers will be asked to bring the vapes and refill materials they plan to use over the next 2 weeks.

Informed Consent: Prior to consenting vapers, trial staff will visually inspect photo identification of vapers to confirm that they are 21 years or older. At the beginning of the first appointment, trial staff will explain the consent form and ask the vaper to read the form. Once the participant has finished reading the form, the trial staff member will ask the participant if he or she has any questions. Then both parties will sign the consent form and the participant will receive a copy of the consent form.

Randomization: At the first visit, trial staff will randomly assign participants to one of the three trial arms by using Qualtrics software. Vapers have an equal chance of being randomized to have labels with control, text, or pictorial warnings.

Assessment: Participants will attend 2 in-person appointments at the study office (at Visit 1 and Visit 3 that are spaced 2 weeks apart). The visits will last about 45-60 minutes. At Visit 1 participants will take a survey, have their vape device and refills labeled based on their trial arm, and take another survey. At Visit 3, participants take a survey and have their vape device and refills labeled based on their trial arm. Participants will also be emailed 3 more surveys to complete online at home (taken at Visit 2, 4, and 5). Thus participants will take 5 weekly surveys overall.

Detailed description of the intervention: At each in-person appointment, participants will bring in the vapes and refills they plan to use over the next 2 weeks for labeling. While participants are taking the survey, trial staff will label the devices and refills based on their trial arm.

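### The by-visit comparison of quit intentions sets one arm's mean against another arm's confidence interval, which with 95% intervals marks about 17% of null pairs as apart instead of 5%

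*SAP*

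**What the plan says.** After setting out the primary model, the SAP section on the primary trial outcome adds a by-visit description: "For descriptive purposes, we will examine mean vaping quit intentions at each trial visit, calculating the mean and standard error". It then says the arms will be compared graphically at each time point, by "examining whether means for each trial arm fall outside of the confidence interval for the other arms". There are five time points: post-labeling at Visit 1, then weeks 1 to 4.

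The SAP gives no confidence level for these intervals and does not say whether a mean must lie outside one of the other intervals or both. It plans no interval for a between-arm difference at a visit. The only general level is at the head of the Analytic plan: "Statistical analyses will use two-tailed tests and a critical alpha of .05".

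The confirmatory analysis is separate: a general linear model on each participant's average across visits, with text as the reference arm. It serves the two primary hypotheses: "We hypothesize that text warnings will elicit higher vaping quit intentions than control messages" and "We also hypothesize that pictorial warnings will elicit higher vaping quit intentions than text warnings".

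**The concern.** The SAP could have planned simply to plot arm means with bars. Instead it names a yes/no criterion for comparing arms and applies it at every visit. The criterion uses the wrong yardstick. An interval around one arm's mean describes the uncertainty of that mean alone, whereas the gap between two estimated means carries the uncertainty of both. Holding one mean against the other's interval leaves out half of the variance when the arms are of equal size.

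This is the only place where the SAP compares arms on quit intentions visit by visit, so it will shape any account of when the warnings began to work or whether their effect faded. The rule can make arms look separated at a visit more often than an interval for the difference would. It cannot alter the primary test.

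**Working it through.** The plan states no error rate for this rule, so there is no figure of its own to reproduce.

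**Inputs**

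- Rule: one arm's mean against another arm's own interval (SAP, Primary trial outcome).
- Interval level: 95%, an assumption that matches the SAP's two-sided alpha of .05.
- Allocation: equal. The protocol's Randomization paragraph says "Vapers have an equal chance of being randomized to have labels with control, text, or pictorial warnings". With equal standard deviations (assumed), the arms have about equal standard errors (SE).
- Size: about 1,200 participants (protocol synopsis), so about 400 per arm. This is needed only for the check with estimated SEs.

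**Pairwise reading**

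Under no true difference, the gap between two independent arm means has standard deviation √(SE² + SE²) = √2 × SE. The rule marks the pair when the gap exceeds 1.96 × SE.

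- Effective threshold: |z| > 1.96/√2 = 1.386.
- Rate: 2 × [1 − Φ(1.386)] = 0.166.
- With an interval for the difference: 2 × [1 − Φ(1.96)] = 0.05.

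Sample size cancels out of the first formula. Simulation with estimated SEs and t intervals shows that the direction of reading matters little:

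| Per arm | One named mean outside | Either mean outside | Both means outside |
|---|---|---|---|
| 400 | 16.5% | 17.4% | 15.7% |
| 336 | 16.5% | 17.4% | 15.6% |

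The second row allows for missed visits: the SAP's sample-size paragraph expects 4.2 completed sessions of 5, and 4.2/5 × 400 = 336.

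**Outside both other intervals**

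Conditional on one arm's standardized mean x, each of the other two means lies more than 1.96 SE away with probability p(x) = 1 − Φ(x + 1.96) + Φ(x − 1.96). Integrating φ(x) × p(x)² over x gives 0.050 per arm. By simulation, at least one of the three arms is marked at a visit 14.7% of the time.

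**Other interval levels, pairwise reading**

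| Interval | Null pairs marked | Nominal rate for a difference |
|---|---|---|
| 90% | 24.5% | 10% |
| 95% | 16.6% | 5% |
| 99% | 6.9% | 1% |

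The excess is present at every level.

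**The two hypothesised contrasts together**

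This is the null probability that at least one of text minus control and pictorial minus text is marked. The two share the text arm. The five-visit rows assume complete data and an equal correlation between visits.

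| Setting | Current rule, pairwise | 95% interval for the difference |
|---|---|---|
| One visit | 28.1% | 9.1% |
| Any of five visits, correlation .9 | 47% | 18% |
| Any of five visits, correlation .7 | 62% | 26% |
| Any of five visits, correlation .5 | 72% | 31% |

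The right-hand column is ordinary multiplicity from unadjusted intervals. The gap between the columns is the effect of the rule.

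**The case against.** The strongest reply is that nothing is decided here. The paragraph is labelled descriptive, the SAP never says that an arm outside an interval will be called different, the hypotheses concern the four weeks as a whole, and they are tested by a separate model. This stands, and it limits the point to how one display is read. It does not rescue the rule: a descriptive comparison should still use the uncertainty of the quantity compared.

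Second, the 17% depends on a level and a reading that the SAP leaves open. This also stands. The level changes the size but not the direction. The outside-both reading does bring the per-arm rate down to about 5%, but about 15% of visits would still show some arm as separate, and that reading does not address the two hypothesised contrasts one by one.

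Third, it might be enough to state the level and say that the display supports no inference. That would be an improvement, but it would leave a faulty comparison rule in the plan.

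Fourth, ten unadjusted intervals can also be over-read, and they leave out pictorial versus control, which the graph covers. Both are true. The remaining multiplicity is shown above and should be stated in the report. The two contrasts proposed are the ones the SAP hypothesises about; the third could be added on the same terms.

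**Conclusion.** The concern holds and is minor. Read pairwise with 95% intervals and equal SEs, the rule marks 16.6% of null pairs at a visit, about three times the 5% given by an interval for the difference. If a mean must lie outside both other intervals, the rate is about 5% per arm and about 15% for any arm at a visit.

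The result rests on two assumptions: the 95% level, which the SAP does not state for this display, and similar SEs, which equal allocation supports. It does not depend on the sample size. The consequence is confined to the by-visit display; the primary and secondary models and their alpha are untouched.

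**What to change.** In the SAP's by-visit paragraph, replace the sentence on graphical comparison with:

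> At each visit we will report, descriptively and without multiplicity adjustment, the text minus control and pictorial minus text differences in mean quit intentions, each with a 95% confidence interval for the difference.

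Drop the mean-outside-interval rule. If arm means are still plotted, say what the bars show and that they are not used to compare arms. The label matters because the paragraph mentions both a standard error and a confidence interval. One-SE bars read by the same rule would exclude a null mean 2 × [1 − Φ(1/√2)] = 48% of the time.

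The cost is one or two sentences and ten contrasts (two at each of five visits) from data already collected. They are not output of the planned primary model, whose outcome is the average across visits, so the same model with text as reference has to be fitted once per visit. Fewer visits will appear to differ. Even so, under no true difference at least one of the ten intervals would exclude zero about 18% to 31% of the time (between-visit correlation .9 to .5), which is why the intervals should stay labelled descriptive.

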Cognitive elaboration	Continuous, 1-5
Perceived likelihood of illness from vaping	Continuous, 1-5
Negative affect	Continuous, 1-5
Information seeking and sharing	
Attention to warning	Continuous, 1-5
Information seeking	Continuous, 0-6
Number of conversations in past week	Continuous, 0-100
Vaping behavior change	
Vaping reinforcement attitudes	Continuous, 1-5
Uncontrolled vaping	Continuous, 1-5
Number of times forgoing a vape in past week	Continuous, 0-6 times
Made vaping quit attempt (for 24 hours) in past 4 weeks	Dichotomous, 0 or 1
Successful quitting of vaping (at last survey)	Dichotomous, 0 or 1
Unintended effects	
Inaccurate risk perception	Continuous, 0% to 100%
Stigma	Continuous, 1-5
Smoking quit intentions among dual users	Continuous, 1-5
Made smoking quit attempt (for 24 hours) in past 4 weeks among dual users	Dichotomous, 0 or 1

Table 1. Secondary outcomes

Edit 6/24/2024: In Table 1, changed range of values for information seeking from "Continuous, 1-5" to "Continuous, 0-6". Changed range of values for number of conversations in past week from "Continuous, 1-5" to "Continuous, 0-100". These updates align this document with the main trial registry.

References

Brewer, N. T., Queen, T., Sheldon, J. M., Lazard, A. J., Ribisl, K. M., Ebrahimi Kalan, M., & Hall, M. G. (In preparation). Impact of e-cigarette warnings on perceived message effectiveness.

- Brewer, N. T., Jeong, M., Hall, M. G., Baig, S. A., Mendel, J. R., Lazard, A. J., ... & Ribisl, K. M. (2019). Impact of e-cigarette health warnings on motivation to vape and smoke. *Tobacco Control*, *28*, e64-e70.
- Brewer, N. T., Hall, M. G., Noar, S. M., Parada, H., Stein-Seroussi, A., Bach, L. E., ... & Ribisl, K.
 M. (2016). Effect of pictorial cigarette pack warnings on changes in smoking behavior: A randomized clinical trial. *JAMA Internal Medicine*, *176*, 905-912.

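### As the SAP is worded, successful quitting of vaping (a 0/1 outcome) gets the general linear model, whose pooled variance gives wrong standard errors, in either direction, when arm quit rates differ

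*SAP*

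**What the plan says.** Under Secondary trial outcomes the SAP sets a default: "Except as noted below, we will again estimate a general linear model for each secondary outcome shown in Table 1", with trial arm as a three-level predictor and text as the reference.

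The model exception is in the next paragraph: "Vaping quit attempt and cigarette smoking quit attempts will each be dichotomous outcomes (any quit attempt during the trial". For these the plan is: "We will estimate a logistic regression model with quit attempt as the outcome and trial arm as the categorial predictor".

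Table 1 types three outcomes as dichotomous, 0 or 1:

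- "Made vaping quit attempt (for 24 hours) in past 4 weeks"
- "Made smoking quit attempt (for 24 hours) in past 4 weeks among dual users"
- "Successful quitting of vaping (at last survey"

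The first two match the exception. The third has its own row, and no sentence in the protocol or SAP gives it a model by name.

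On missing data for secondary outcomes the SAP says: "We will handle missingness as we did for the primary outcome". For the primary outcome that means averaging whatever is available and, for a participant with no data, "we will set their value to the grand mean for the trial overall (ignoring trial arm".

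**The concern.** Successful quitting is the only Table 1 outcome that measures vaping cessation; the quit-attempt row records a 24-hour attempt. It belongs to the vaping behavior change group, for which the SAP hypothesizes text above control and pictorial above text.

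A general linear model uses one residual variance for all arms. For a 0/1 outcome the variance in an arm is p(1 − p), so arms with different quit rates have different variances. Each pairwise contrast then borrows variance from the third arm, which may be larger or smaller than its own. The SAP states no robust or unequal-variance option. If the hypothesized ordering is true, the two planned contrasts are distorted in opposite directions.

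Leaving the model unnamed also lets an analyst choose between two defensible readings, with different p-values, after seeing the data.

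**Working it through.** **Inputs.** Equal allocation to three arms (protocol, Randomization); about 1,200 participants (protocol synopsis), so 1,200/3 = 400 per arm; two-sided alpha of .05 (SAP, Analytic plan). The plan has no quit rate and no power figure for this outcome, so there is nothing of its own to reproduce. All quit rates below are assumptions, in the order control/text/pictorial.

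**Formulas.** Let v = p(1 − p) in each arm and n be the number per arm.

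- Squared SE from the linear model, any contrast: 2V/n, with V = (v_C + v_T + v_P)/3.
- The contrast's own squared SE for arms a and b: (v_a + v_b)/n = 2W/n, with W = (v_a + v_b)/2.
- Ratio of the two SEs: R = √(V/W). The sample size cancels.
- Actual rejection rate when the two compared arms are truly equal: 2 × [1 − Φ(1.96 R)].

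**Pictorial vs text, these two equal, control lower**

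| Assumed rates | V | W | R | Rejection |
|---|---|---|---|---|
| 20/25/25% | (.1600 + 2 × .1875)/3 = .1783 | .1875 | 0.975 | 5.6% |
| 5/8/8% | (.0475 + 2 × .0736)/3 = .0649 | .0736 | 0.939 | 6.6% |
| 3/8/8% | (.0291 + 2 × .0736)/3 = .0588 | .0736 | 0.894 | 8.0% |
| 2/6/6% | (.0196 + 2 × .0564)/3 = .0441 | .0564 | 0.885 | 8.3% |

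**Text vs control, these two equal, pictorial higher**

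| Assumed rates | V | W | R | Rejection |
|---|---|---|---|---|
| 10/10/15% | (2 × .0900 + .1275)/3 = .1025 | .0900 | 1.067 | 3.6% |
| 5/5/10% | (2 × .0475 + .0900)/3 = .0617 | .0475 | 1.139 | 2.55% |
| 3/3/8% | (2 × .0291 + .0736)/3 = .0439 | .0291 | 1.229 | 1.6% |

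**All arms equal.** V = W, so R = 1 and the rejection rate is 5%.

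**Hypothesized ordering, 3/5/7%.** V = (.0291 + .0475 + .0651)/3 = .0472.

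- Text vs control: W = .0383, R = 1.111, so the SE is 11% too large.
- Pictorial vs text: W = .0563, R = 0.916, so the SE is 8% too small.

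**Check by simulation** (400 per arm, 200,000 trials per scenario), linear model against logistic likelihood ratio test:

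- 2/5/5%, pictorial vs text (true null): 7.9% against 5.3%. The linear model's 95% interval covers 92.1%.
- 5/5/10%, text vs control (true null): 2.5% against 5.4%.
- 3/5/7%: rejection for text vs control 23% against 31%, and for pictorial vs text 28% against 23%. The last apparent gain comes from an SE that is too small.
- For true-null contrasts across the scenarios simulated, the logistic likelihood ratio test rejects 4.9% to 5.6% of the time, and the risk difference with an unpooled SE 4.7% to 5.1%.

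**Missing data.** I read the last survey as the week 4 survey, so the outcome is measured once and there is nothing to average over. A participant without it would receive the overall mean. At 3/5/7% with equal arms that is (.03 + .05 + .07)/3 = .05, which is not a valid 0/1 response for a standard binary logistic model.

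**The case against.** The strongest reply is that this is an omission, not a chosen analysis. The linear model that the SAP carries over was specified for a continuous outcome. Table 1 types successful quitting exactly as it types the two outcomes given logistic regression, and an analyst could reasonably infer logistic here too. That stands as an account of intent. It does not settle the wording: the default covers every Table 1 outcome unless excepted, and the Table 1 column gives variable type and range, not a model.

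A reader might infer more than the documents support:

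- **That the test generally runs at about 8%.** This needs text and pictorial to be equal, control lower, and a large gap. On the logit scale (d = ln OR × √3/π), 3% vs 8% is an odds ratio of about 2.8 and d of about 0.57, against the SAP's planning d of .16. That planning value concerns pictorial vs text, and the SAP says only that control vs text was larger, so it is a benchmark and not a forecast. With control rates of 2% to 10%, the formula above gives 5.8% to 6.0% at d = 0.16 and 6.5% to 6.9% at d = 0.32.
- **That the error always favors the warnings.** It also runs the other way, as the text-vs-control rows show.
- **That the estimated effect is biased.** With arm as the only predictor and complete data, the linear model returns the arm proportions and their differences exactly.
- **That the trial's main result is affected.** This is one of 16 secondary outcomes; the primary is quit intentions.

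It is also fair to say that reporting a mean difference beside odds ratios is a matter of presentation, and that the two quit-attempt outcomes already have a suitable model.

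**Conclusion.** The point holds as a gap in the SAP's wording with a real but moderate consequence. Followed as written, the plan gives successful quitting a standard error, interval and p-value that are wrong whenever arm quit rates differ. Under the rates assumed here, a nominal 5% test of equal arms rejects about 5.6% to 8.3% of the time for pictorial vs text when control is lower. For text vs control it rejects about 1.6% to 2.5% at 3/3/8% and 5/5/10%, and 3.6% at the milder 10/10/15%. These ranges describe the assumed scenarios and are not bounds; smaller gaps give smaller errors, and equal rates give none. The direction and mechanism follow from the model and do not depend on the assumed rates. The change is worth making because it is cheap and the outcome is the trial's only measure of vaping cessation.

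**What to change.** 1. Add successful quitting of vaping to the logistic regression sentence, with text as the reference arm. State which test will be used: at low rates the Wald test was conservative in the simulation (3.5% for text vs control at 2/2/4%, against 5.6% for the likelihood ratio test).
2. For this outcome, report the percentage quitting in each arm and the risk difference with an unpooled (robust) interval.
3. State that grand-mean substitution does not apply to it, and give a rule that yields valid 0/1 data. For example, analyze observed responses, with a sensitivity analysis that counts missing as not quit. Say whether the last survey means the week 4 survey or each participant's last completed one.

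The cost is a sentence or two in the SAP and a little extra analysis. Data collection does not change. The edit should be dated and, if it comes after quit rates by arm have been seen, reported as such.
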